10.9.1 Study Exit

A study exit eCRF is required for all subjects. Prior to exiting a subject from the study, it is recommended

to follow the subject until all ongoing system and/or procedure related AEs are resolved or unresolved with no further actions planned.

Following exit, subjects will continue to receive standard medical care. Upon exiting from the study, no further study data will be collected, or study visits will occur for the subject. All data available through the time of the subject's exit will be used for analysis.

Subjects are urged to remain in the study as long as possible but may be exited from the study for any of the following situations:

- Study completed
- Subject lost to follow-up
- Subject death
- Subject did not meet inclusion/exclusion criteria
- Subject did not provide consent (or data use protection authorization)
- Subject chooses to withdraw (e.g., consent withdrawal, relocation to another geographic location)
- Investigator deems withdrawal necessary (e.g., medically justified, inclusion/exclusion criteria not met, failure of subject to maintain adequate study compliance)

The following information is required to be collected at study exit:

- Reason for exit

If discontinuation is because of safety or lack of effectiveness, the subject shall be asked to be followed for collecting safety data outside the clinical investigation.

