9.2 Subject Enrollment

A subject is considered enrolled in the study when the consent process is signed and dated. Screening data will not be collected for the study until the subject has been determined to be eligible for the study and signed consent (see **Section 10.2** for details). If the subject is consented prior to the day of surgery, a re-verification of eligibility will be signed off by the PI or Sub-I on the day of surgery. As soon as the surgical procedure has begun with the Medtronic Hugo™ RAS System, the subject must be followed

Medtronic Business Restricted

This document is electronically controlled

CONFIDENTIAL 056-F275 Rev E Clinical Investigation Plan Template

regardless of whether or not the subject completed the surgical procedure with the Medtronic Hugo™ RAS System. Subject enrollment will be consecutive at the institution according to required procedure types and eligibility criteria. See **Section 9.3** for additional details.

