10.9 Subject Exit, Withdrawal or Discontinuation

Subjects may voluntarily withdraw from the study at any time. Additionally, the Principal Investigators may withdraw or choose not to enroll subjects if they feel they do not meet the CIP defined inclusion and exclusion criteria or if it is in the best medical interest of the subject in question. If the study Investigator voluntarily removes a subject from further study participation, supporting documentation must be in place for the rationale and date of removal.

Every attempt will be made to contact subjects who are noncompliant. Subjects will be considered lost to follow-up once the following steps have been taken:

- Three phone calls should be made to the subject. Each attempt should be clearly documented in the source documents and the response or lack thereof should be captured.
- If there is no response to the phone calls, then a certified/registered letter should be written to the subject. A copy of the letter should be retained in the subject's source document.
- After a period of two weeks following completion of the above actions, the subject will be considered lost to follow-up. The sponsor should be notified and the Study Exit form should be completed.

In cases of early study exits, all data collected from the time of informed consent to the time of exit may be used. Subjects who exited early will not be replaced. Enrollment will continue as per CIP definitions up to the predefined maximum number of subjects.

The reason and date for study exit of all enrolled subjects will be documented on the applicable electronic case report form (eCRF).

All subjects will be followed per institutional standard of care after any withdrawal, discontinuation, or completion of the study follow-ups.

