10.9.5 Investigator Withdraws Subject

No subjects should be withdrawn by Investigators unless compelling medical justification is present. It is recommended investigators discuss any withdrawals with the study team prior to withdrawing subjects. If an Investigator withdrawal is necessary, the following data should be collected prior to subject withdrawal if possible:

- Reason for subject withdrawal

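### Exit for unmet eligibility criteria is not limited to before first incision, so a late first major complication in a treated subject could go uncollected

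*Protocol*

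**What the plan says.** Four places in the protocol deal with a treated subject who is later judged ineligible.

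- **9.2 Subject Enrollment:** "As soon as the surgical procedure has begun with the Medtronic Hugo™ RAS System, the subject must be followed", whether or not the operation is finished with Hugo.
- **10.9 Subject Exit, Withdrawal or Discontinuation:** Principal Investigators "may withdraw or choose not to enroll subjects if they feel they do not meet the CIP defined inclusion and exclusion criteria". No time limit is attached.
- **10.9.1 Study Exit:** unmet criteria appear twice among the exit reasons, once on their own and once as "Investigator deems withdrawal necessary (e.g., medically justified, inclusion/exclusion criteria not met, failure of subject to maintain adequate study compliance". Neither entry is tied to the period before incision. On the effect of exit: "Upon exiting from the study, no further study data will be collected, or study visits will occur for the subject". The next sentence adds: "All data available through the time of the subject's exit will be used for analysis".
- **10.9.5 Investigator Withdraws Subject:** "No subjects should be withdrawn by Investigators unless compelling medical justification is present".

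The analysis rules bear on the same subject. Protocol 14.9 and SAP 7.1.3 fix membership of the full analysis set (FAS) at first skin incision. Protocol 10.8 gives unmet criteria as an example of a deviation. SAP 7.1.3 counts it as a major deviation, whose consequence is exclusion from the per protocol set (PPAS), not from the FAS.

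**The concern.** For a treated subject later judged ineligible, a site can point to one rule that requires follow-up and another that permits exit. If the site uses exit, collection stops and a later event within 30 days may never reach the database.

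The endpoint at stake is the primary safety endpoint, the proportion of subjects with a Grade III or higher complication through day 30. The primary effectiveness endpoint is not exposed, because conversion is settled at the index procedure. The study is single-arm and open-label, and the investigator at the site makes the exit decision.

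The analysis would not correct for such a loss. The primary analysis does not impute (Protocol 14.11, SAP 7.4). Multiple imputation for safety starts only above 5% missing (SAP 7.9.2.7). SAP 7.12 rules out a tipping-point analysis for safety. The SAP also does not say how an FAS subject with no recorded event who exits before day 30 is counted.

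**Working it through.** **Step 1. Which events can be lost?**
- A Grade III or higher event recorded before exit stays in the analysis (10.9.1). The endpoint is per subject, so that subject already counts, and a further event after exit changes nothing.
- For an event already open at an early exit, 12.3 asks for efforts to keep following it if it is unresolved and related to the system or procedure. It does not reach new events. It also leaves out events related only to the underlying condition, which SAP 7.9.2.2 counts in the endpoint.
- The safety follow-up at the end of 10.9.1 applies to discontinuation for safety or lack of effectiveness, and takes place outside the investigation.
- What remains is a treated subject whose first Grade III or higher event arises after an eligibility exit and by day 30.

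**Step 2. Reproduce the plan's power** (inputs from Protocol 14.4.2). The test is exact binomial and one-sided, with α = 0.025/3 = 0.0083 at the first Holm step. The pass limit c is the largest count with P(X ≤ c | n, goal) ≤ α, and power is P(X ≤ c | n, expected rate).
- Nephrectomy and prostatectomy: n=49, goal 20%, expected 2.9%. c=3 (P=0.0067), power 94.7% (stated 95%).
- Cystectomy: n=27, goal 45%, expected 14.1%. c=5 (P=0.0038), power 82.9% (stated 83%).

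**Step 3. Lose one event at the first Holm step.** The subject is either kept as event-free or dropped from the denominator.

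| Cohort | True result | Kept as event-free | Dropped |
|---|---|---|---|
| Nephrectomy or prostatectomy, full n=55 | 4/55, p=0.0087, fails | 3/55, p=0.0024, passes | 3/54, p=0.0029, passes |
| Same, after attrition n=49 | 4/49, p=0.0214, fails | 3/49, p=0.0067, passes | 3/48, p=0.0079, passes |
| Cystectomy, full n=31 | 7/31, p=0.0085, fails | 6/31, p=0.0027, passes | 6/30, p=0.0040, passes |
| Same, after attrition n=27 | 6/27, p=0.0125, fails | 5/27, p=0.0038, passes | 5/26, p=0.0058, passes |

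**Step 4. Later Holm steps.** SAP 7.5 gives 0.025/2 = 0.0125 at step 2 and 0.025 at step 3. At step 2, 4/55 and 7/31 pass with no event lost. At step 3, 4/49 and 6/27 (p=0.01251, just above 0.0125) also pass. Each step has its own limit. At step 3 with n=55, 5 events pass (p=0.0245) and 6 fail (p=0.0576). Losing one of the 6 gives a pass if the subject is kept as event-free. If the subject is dropped, the limit at n=54 is 4, so 5/54 fails. With n=31, 8 pass (p=0.0226) and 9 fail (p=0.0522); 8/31 passes, but the limit at n=30 is 7.

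**Step 5. Chance of being at the first-step boundary at the planned rates.**
- Exactly 4 of 55 at 2.9%: C(55,4) × 0.029⁴ × 0.971⁵¹ ≈ 0.05.
- Exactly 7 of 31 at 14.1%: C(31,7) × 0.141⁷ × 0.859²⁴ ≈ 0.08.

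The post-exit event in Step 1 would be needed as well.

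**Step 6. The 5% trigger.** 5% of 55 is 2.75, of 31 is 1.55, and of 141 is 7.05. Two, one and seven missing subjects respectively stay below it, so a loss that changes a result need not start the imputation analysis.

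**The case against.** The strongest reply is that the eligibility exit is meant for the period before surgery. Enrollment happens at consent, so subjects who fail afterwards need an exit reason. Protocol 10.4 tells subjects that screening may show them unsuitable, and the example in 14.9 concerns ineligibility arising between consent and the procedure day. When consent came earlier, eligibility is re-verified on the day of surgery. Section 10.9.5 discourages investigator withdrawal, and 10.9.6 prefers reduced data collection to exit. SAP 7.12 considers missing safety data unlikely because the endpoint would require hospitalization. All of this stands as evidence that late eligibility exits should be rare. It does not settle the text: 10.9 and 10.9.1 state no time limit, and the medical-justification condition in 10.9.5 itself conflicts with the eligibility reason in 10.9.1.

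A reader might go further and infer that subjects who do badly will be declared ineligible and disappear from the safety result. The documents do not support that. Complications recorded before exit are kept, and FAS membership does not change. Exclusion 3 refers to a bleeding disorder that has been diagnosed, so one uncovered by an operative bleed fits its wording poorly. Exclusion 8 concerns active infection, so sepsis after surgery would ordinarily be an adverse event rather than proof of earlier ineligibility. Exit driven by outcome is possible under a discretionary rule, but nothing shows that it will occur.

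A reader might also infer that one lost event decides a cohort in general. It does so only at a boundary, and the first-step limit does not bind a cohort once another has passed at that step.

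**Conclusion.** The contradiction is real: 10.9 and 10.9.1 permit what 9.2 forbids, and 10.9.5, 10.8 and SAP 7.1.3 fit 9.2. It needs a minor to moderate reconciliation. It does not by itself undermine the safety analysis.

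The possible loss is confined to first Grade III or higher events after an eligibility exit and by day 30. The documents give no frequency for such exits; I assume they are rare. If one occurs in a cohort at the first-step limit, the result can turn from fail to pass at both the full and the attrition-adjusted sample sizes. At the planned event rates, a cohort at full size sits exactly there in roughly 5% (nephrectomy or prostatectomy) or 8% (cystectomy) of trials, before allowing for the rarity of the exit. At the last Holm step the result also depends on how the exited subject is counted, which the SAP leaves open.

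**What to change.** Reconcile Protocol 9.2, 10.9, 10.9.1 and 10.9.5:

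1. In 10.9 and in both eligibility entries of 10.9.1, limit exit for unmet inclusion or exclusion criteria to the period before first skin incision.
2. State that a treated subject later found ineligible is recorded as a protocol deviation, stays in the FAS, completes scheduled follow-up (day 30, and years 1 to 5 if oncologic) unless the subject withdraws consent, and is excluded only from the PPAS.

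The cost is protocol wording and the usual amendment approvals. It adds no visit that 9.2 does not already require, and the SAP analysis sets stay as they are. It should be done while subjects are still being treated, because analysis cannot restore events that were not collected.

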12.3 Processing Updates and Resolution

For any changes in status of a previously reported adverse event or DD (i.e., change in actions taken, change in outcome, change in relatedness), information needs to be updated on, or added to the original AE or DD form. All AEs must be followed until the AE has been resolved, is unresolved with no further actions planned, the subject dies or exits the study, whichever occurs first.

In the event that a subject is exited from the study prior to study completion, all efforts should be made

to continue following the subject until all unresolved system or procedure related AEs, as classified by the Investigator, are resolved or unresolved with no further actions planned.

At the time of study exit, all collected adverse events that are unresolved must be reviewed and an update to the original AE must be reported.

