14.4.2 Primary Objective #2 (Safety)

The primary safety objective of this study is to confirm that the Medtronic Hugo™ RAS System is safe when used for urologic robotic assisted surgery. The primary safety endpoint is the rate of subjects with major complications (meeting Grade III criteria or higher per the Clavien-Dindo Classification system) from the first incision through 30 days post-procedure. Further details can be found in **Section 6.4.2**.

The primary safety hypothesis is to test the overall 30-day major complication rate (i.e., rate of subjects with one or more major complications) against a performance goal. Since the safety profiles or major complication rates are very different among the three surgeries, a separate performance goal is pre-specified for each of the three surgery types (as per FDA recommendation). The performance goals are determined based on published literature data.

Let R be the 30-day major complication rate, and PG be performance goal for a specific surgery group. The statistical hypothesis is formulated as follows:

$$H_0: R \geq PG \text{ vs. } H_a: R < PG$$

The hypothesis will be tested using the Clopper-Pearson exact method and the null hypothesis will be rejected if one-sided p-value is significant comparing to alpha determined after multiplicity adjustment as described in **Section 14.12**.

Performance Goal Rationale and Sample Size

The literature search was performed based on available literature for each of the three surgery types (nephrectomy, prostatectomy, cystectomy). Point estimates along with 95% and 99% predicted intervals were calculated to provide plausible range of potential effect sizes. Clinically meaningful margins and statistical precisions have been taken into account to determine the appropriate performance goals. In some situations, considerations were also given to align with the studies from comparable sample sizes. The calculation details and rationales are summarized in the following table.

All sample size calculations are based on exact test. Presuming a one-sample proportion and one-sided test with the least alpha of 0.008 (0.025/3) when performing three hypothesis testing (nephrectomy, prostatectomy, and cystectomy, respectively) and adjusting for multiplicity in primary safety objectives, sample size justification and performance goals are described as below:

Surgery Type	Performance Goal (PG)	Sample Size	Rationale

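### A new Grade III or higher event that starts after a safety-related study exit and before day 30 has no documented route into the primary safety analysis

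*Protocol*

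**What the plan says.** Protocol 10.9.1 (Study Exit) makes three linked statements.

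- For every exit: "Upon exiting from the study, no further study data will be collected, or study visits will occur for the subject".
- For the analysis: "All data available through the time of the subject's exit will be used for analysis".
- Where discontinuation "is because of safety or lack of effectiveness, the subject shall be asked to be followed for collecting safety data outside the clinical investigation".

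The primary safety endpoint in Protocol 14.4.2 runs "from the first incision through 30 days post-procedure". SAP 7.9.2.2 derives it from the AE start date, the Clavien-Dindo grade and the CEC-adjudicated relatedness.

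Other sections pull the other way.

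- Section 9.2: "As soon as the surgical procedure has begun with the Medtronic Hugo™ RAS System, the subject must be followed", whether or not the operation is completed with Hugo.
- Section 10.9.6 prefers reduced data collection to exit.
- Section 12.3 asks sites, after an early exit, "to continue following the subject until all unresolved system or procedure related AEs, as classified by the Investigator, are resolved" or need no further action. The same section also lists study exit as a point at which AE follow-up ends.

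On missing data, SAP 7.4 applies no imputation in the primary analysis. SAP 7.9.2.7 uses multiple imputation for safety only above 5% missing. SAP 7.12 rules out a tipping-point analysis for safety.

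**The concern.** The device is used once, on Day 0. After surgery there is no study treatment left to stop, so a treated subject's discontinuation for safety gives no evident reason to move the remaining days of safety follow-up out of the trial. Followed literally, section 10.9.1 asks for the information and then places it where the endpoint derivation cannot use it.

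The affected group is selected for having had a safety problem or a device failure, so the loss cannot be assumed unrelated to outcome. Each safety test is an exact binomial test on 55 or 31 subjects at most, and its result can turn on one event. The 30-day readmission and reoperation rates are exposed in the same way.

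**Working it through.** **1. The plan's own figures.** The rule is the largest count c with P(X ≤ c | n, goal) ≤ α, and power is P(X ≤ c | n, assumed rate). Inputs are from Protocol 14.4.2, with α = 0.025/3 = 0.0083; using 0.008 gives the same c.

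- Nephrectomy and prostatectomy: n = 49, goal 0.20, rate 0.029. c = 3, exact α = 0.0067, power 94.7% (stated 95%).
- Cystectomy: n = 27, goal 0.45, rate 0.141. c = 5, exact α = 0.0038, power 82.9% (stated 83%).

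Both reproduce. Nothing here changes sample size or power.

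**2. Which events are lost.**

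| Event | Route into the endpoint |
|---|---|
| Grade III or higher, began before or prompted the exit | Counted by AE start date (SAP 7.9.2.2) |
| AE open at exit that later worsens | Follow-up requested by 12.3 if system- or procedure-related |
| Death | Own reporting rules (12.1, 12.6) |
| New non-fatal Grade III or IV event starting after exit, by day 30 | None documented |

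**3. How an early exit is counted.** SAP 7.9.1.6 drops subjects with a missing conversion outcome, and SAP 7.9.3.6 uses FAS subjects with data available. SAP 7.9.2.6, for safety, only says that FAS subjects are included. It does not say whether a subject who leaves event-free before day 30 is a non-event or missing, so both are computed.

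**4. Effect of one lost event.** One-sided p = P(X ≤ x | n, goal), at full enrollment. Holm limits are 0.025/3 = 0.0083, 0.025/2 = 0.0125 and 0.025, applied to the smallest, middle and largest p-value.

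| Limit | True count | One lost, kept as non-event | One lost, excluded |
|---|---|---|---|
| 0.0083 | 4/55: 0.0087 fail | 3/55: 0.0024 pass | 3/54: 0.0029 pass |
| 0.0083 | 7/31: 0.0085 fail | 6/31: 0.0027 pass | 6/30: 0.0040 pass |
| 0.0125 | 5/55: 0.0245 fail | 4/55: 0.0087 pass | 4/54: 0.0101 pass |
| 0.0125 | 8/31: 0.0226 fail | 7/31: 0.0085 pass | 7/30: 0.0121 pass |
| 0.025 | 6/55: 0.0576 fail | 5/55: 0.0245 pass | 5/54: 0.028 fail |
| 0.025 | 9/31: 0.0522 fail | 8/31: 0.0226 pass | 8/30: 0.031 fail |

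**5. Type I error at the 0.025 step, subject kept as a non-event.** The extreme case, one event lost every time, moves the limit from c to c + 1. For n = 55, P(X ≤ 5) = 2.45% becomes P(X ≤ 6) = 5.8%. For n = 31, P(X ≤ 8) = 2.3% becomes P(X ≤ 9) = 5.2%. A milder case loses a share m of true events, giving P(X ≤ c | n, goal × (1 − m)). The documents give no m; a range of 0 to 10% is assumed.

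| m | n = 55 | n = 31 |
|---|---|---|
| 0 | 2.5% | 2.3% |
| 2% | 2.9% | 2.9% |
| 5% | 3.6% | 4.0% |
| 10% | 5.3% | 6.6% |

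**6. Whether a planned sensitivity analysis would show it.** 5% of 141 is 7.05, so up to 7 missing subjects leave imputation untriggered. Taken by cohort, one missing subject is 1/55 = 1.8% or 1/31 = 3.2%, again below 5%. There is no safety tipping-point analysis.

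**The case against.** The strongest reply is that the gap is narrow and the affected subjects few. Section 9.2 keeps converted subjects in follow-up, so stopping use of Hugo during surgery is not an exit. Section 10.9.5 reserves investigator withdrawal for compelling medical reasons, section 10.9.6 prefers modified collection, and section 10.9.1 itself recommends following related AEs to resolution before exit. All of this stands. It limits the number affected but gives no route for the new event in step 2.

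A second reply is that the wrong sentence is blamed: the general exit rule causes the loss for every kind of exit. That also stands. The sentence on safety discontinuation fails to repair the loss in the group where repair matters most and where follow-up is already to be requested.

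A third reply is that excluding early exits removes the effect at the 0.025 step, and that excluding an event-free exit raises the observed rate. This is correct, but the SAP does not choose that handling, and at the first two Holm limits the flip remains.

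Three stronger inferences are not supported:

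- **That post-exit events never reach the endpoint.** Section 12.3 and the AE start-date rule bring some of them in.
- **That the type I error roughly doubles.** This needs one event lost every time, the subject kept as a non-event, and a true rate equal to the goal. At the design rates, exactly 6 events in 55 has probability 0.4% and exactly 9 in 31 has 1.6%.
- **That the sponsor holds these data and leaves them out, or that the deaths vanish.** The protocol only says that the subject is asked, and deaths have their own reporting rules.

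**Conclusion.** The point holds in a limited form. Under section 10.9.1 as written, a new non-fatal Grade III or higher event starting after a discontinuation for safety or lack of effectiveness, and before day 30, has no documented route into the primary safety analysis. This fits poorly with sections 9.2, 10.9.6 and 12.3.

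The documents give no rate for such exits beyond the general 10% attrition allowance, and few are to be expected. One lost event matters only when a cohort sits at its boundary. There it can change the result at the first Holm step under either handling, and at the 0.025 step only if the subject is kept as a non-event. The 5.8% and 5.2% figures are extreme upper bounds under that handling, not estimates. The plan's power figures stand. The change is worth making because the loss falls on a group selected for safety problems, no planned analysis would reveal a few such losses, and the repair is small.

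**What to change.** **Protocol.** Reconcile sections 9.2, 10.9.1, 10.9.6 and 12.3 so that they say the same thing: a treated subject discontinued for safety or lack of effectiveness, who has not withdrawn consent, remains in the study's own safety data collection through day 30. AEs with Clavien-Dindo grade, readmission, reoperation and vital status go on the eCRF, events requiring adjudication go to the CEC, and the data enter the primary and 30-day secondary safety analyses. For these subjects, remove the provision that places their safety data outside the investigation.

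**SAP.** In 7.9.2.6, state how a subject who exits event-free before day 30, for any reason, enters the numerator and denominator. This is needed whatever is done to the protocol, because exits for other reasons will remain.

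**Cost.** A protocol amendment, with the approvals that section 16.6 requires; a little more data entry and adjudication for a few subjects; and observed safety rates that may be slightly less favourable. Sample size, goals and tests do not change.
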